**1) Protocol Abstract** (*Briefly (in 250 words or less) describe the study in language understandable to a layperson. Include a brief description of the study purpose, target disease/condition if applicable, key eligibility criteria, and main study interventions*): Kidney biopsy is the primary technique to assess the degree of kidney damage and disease progression. However, this procedure is costly and has complications including bleeding, infection and patient discomfort. It is also impractical to perform biopsies on patients who are ill or have bleeding tendencies. The ultrasound technique has been used for many years to assess kidney structure and status. However, it is not accurate or reliable at quantifying the degree of fibrosis (long term damage) of diseased kidneys. Interestingly, a promising new ultrasound technique called shear wave elastography (SWE) has been developed to assess tissue stiffness. This technique has been studied previously in transplanted kidneys with promising results. It has only been done in few studies on native kidneys and these studies had major limitations. Our study will attempt to build upon these prior studies and overcome their shortcomings by comparing results obtained by SWE across a broad range of patients with kidney disease as assessed by biopsy results. We are aiming to determine whether SWE can serve as a non-invasive marker of kidney fibrosis. This technique can serve as a marker to follow up the rate of progression of kidney disease besides laboratory tests. More importantly, SWE has the potential to revolutionize practice by helping clinicians make decisions about getting a kidney biopsy.

**2) Project Objectives and Hypotheses:** Objective: To determine whether differences exist in elasticity measurements between native kidneys with and without fibrosis.  
Hypothesis: Kidneys with higher grades of fibrosis will demonstrate higher (up to x 1.5) measures of tissue elasticity and stiffness compared to kidneys with zero fibrosis.

 Einstein HEALTHCARE NETWORK	AEHN Protocol/Summary		
	NUMBER	DATE	PAGE
	HRP-204	12/27/2012	2 of 13

**3) Background/Significance of Research** (*Provide the scientific or scholarly background and rationale for the research based on the existing literature (include references). Describe relevant prior experience and gaps in current knowledge. Describe any relevant preliminary data. Explain the significance of the research in terms of why it's important and how it will add to existing knowledge.*): Chronic kidney disease (CKD) is a major public health problem with over 19 million adults in the US diagnosed with early CKD and 640,000 adults with end stage renal disease (ESRD) [1-5]. Currently, CKD is staged based formulas derived by creatinine values. Limitations of such measures include confounding factors such as age, race and muscle mass. Acute kidney injury (AKI) on the other hand is an abrupt deterioration in renal function with or without reduced urine output. Using lab values to distinguish acute and chronic kidney disease can be impossible even to the trained physician, however their pathogenesis and treatment are different highlighting the need for an accurate diagnosis. Fibrosis is the common final pathway of CKD, with the degree of fibrosis directly related to severity [6, 7]. Acute processes on the other hand lead to inflammation or tubular dysfunction in the absence of fibrosis. Until now, the gold standard for diagnosing intrinsic kidney disease remains to be a biopsy. Kidney biopsies are usually indicated when pre renal or post renal causes of AKI have been excluded and a cause of the intrinsic renal dysfunction remains elusive. However, kidney biopsies are not without their disadvantages which include cost, risks related to its invasive nature and sampling error [8-11]. There are also instances, such as the acutely ill patient or those with bleeding tendencies, when a biopsy is contraindicated. Therefore, it seems prudent to develop a non-invasive marker for kidney fibrosis that would aid clinicians to decide about the need to obtain a biopsy. This is the premise of our research project, to determine whether shear wave elastography can be a reliable marker for kidney fibrosis.

Shear wave elastography (SWE) is an emerging technique which permits the non-invasive measurement of tissue elasticity [12]. This technique is now FDA approved for use in liver disease due to its ability to discriminate normal and cirrhotic liver tissue. Similar techniques have been investigated with varied success in other tissues including breast, thyroid and prostate. Studies of SWE have been performed on transplanted renal allografts showing an association between tissue stiffness measured by SWE and kidney fibrosis [13-15]. Transplanted kidneys are more superficial compared to native kidneys; thus estimates of tissue elasticity of transplanted allografts may not apply to native kidneys [16, 17]. Only few studies examined SWE in native kidneys and those had inherent limitations [18-20]. The main limitation being, there was no matchup between kidney fibrosis scores and SWE values. We propose to replicate the studies performed on transplanted kidneys while building upon and improving on the limitations of the prior studies conducted in native kidneys.

Kidney biopsy remains the gold standard for evaluation of kidney fibrosis in patients with abnormal kidney function. However, this invasive procedure is associated with: cost, risk of bleeding, infection, patient discomfort and sampling error. In other scenarios where patients are acutely ill, on anticoagulation or with very low platelet counts biopsies are in-fact contraindicated. SWE as a non-invasive marker of kidney fibrosis has the potential to provide immediate results at little cost with no harm to the patient. It will also likely reduce the rates of unnecessary biopsies and eliminate the complications associated with such an invasive procedure.

SWE is a novel FDA approved technique to assess organ fibrosis. Its successful application in the hepatology community has raised interest about its utility in other organs. We hope to extend the utility of this technique and use it in native kidney disease. Our study's goal is to determine whether SWE can be used as a non-invasive marker of kidney fibrosis. This study may have great clinical ramifications as the field of nephrology is expanding towards the development of non-invasive markers of kidney disease. The results of our study would provide clinicians with a tool that rapidly assesses tissue fibrosis while limiting the need for invasive and risky procedures. Given the clinical and scientific need for this type of research, background of the investigators, identified population and potential for multiple future avenues of research, this project is important, novel, feasible and an excellent use of research resources.

#### **4) Setting of the Human Research:**

- a. Indicate all AEHN locations where the human research will be conducted (check all that apply):

NUMBER	DATE	PAGE
HRP-204	12/27/2012	3 of 13

- Tabor Rd campus  
 Elkins Park campus  
 Belmont Center for Comprehensive Treatment  
 Center One  
 Montgomery campus  
 Other: please specify - [REDACTED]

b. Indicate if human research will be conducted at external location(s) overseen by the AEHN investigator (e.g. private physician office, collaborating hospital/university)

- Yes (Complete Appendix B: External Site Approvals on Application for Human Research)  
 No

## 5) Resources available to conduct the Human Research:

a. Target population (e.g. Adult subjects with a diagnosis of Type II diabetes for greater than two years":  
 Adults over the age of 18 who underwent native kidney biopsy at the Einstein Medical Center in Philadelphia will be eligible for the study

### b. For prospective studies:

- i.) Total number of subjects planned to be enrolled in the study at AEHN site(s): **40**
- ii) For multi-site projects, please indicate total number of subjects planned to be enrolled in the study at all sites: **N/A**
- iii) Describe access to a population that would allow recruitment of the targeted number of subjects (*i.e. how many potential subjects do you have access to? What percentage of those potential subjects do you need to recruit?*) : A list of patients who recently underwent a native kidney biopsy will be obtained from the pathology department on a weekly basis. Our research team will then contact the patients and discuss participation in the project. If they agree, during a follow up visit with the nephrologist formal informed consent will be obtained and questions answered. On a yearly basis, 50-60 native kidney biopsies are performed at AEMC. Therefore, we will need to recruit 80-90% of those patients.

Telephone script: Hello. My name is Dr " " and I am a medical doctor at the Albert Einstein Medical Center. I am calling you with regards to a study we are conducting at our center involving a new ultrasound technique called shear wave elastography. We are recruiting interested subjects who have had a kidney biopsy. You are qualified to participate in the study. If you are interested, your nephrologist will discuss the details of this study with you in greater detail during your follow up visit. Thank you and have a wonderful day.

### c. For retrospective studies:

- i.) Estimated number of charts to be reviewed: **N/A**

 
Einstein HEALTHCARE NETWORK
	AEHN Protocol/Summary		
	NUMBER	DATE	PAGE
	HRP-204	12/27/2012	4 of 13

- ii.) Time period of interest for data being collected (e.g. *Subjects who had XX procedure between 6/1/00 and 6/1/05:* [REDACTED])
- d. Describe the number and qualifications of the study team members, their experience in conducting research, their knowledge of the local study site(s), culture, and society: The study team members include 3 PGY2 residents, 1 PGY4 resident with prior research experience in this field, 1 PGY intern with interest in nephrology, 1 radiology resident PGY3, 1 radiology attending with experience in ultrasound imaging (director of body ultrasound at AEMC) and 1 nephrology attending with vast clinical and research experience.
- e. Describe the time that the investigator and other study team members, if applicable, will devote to conducting and completing the study within the anticipated study period (e.g. *10% of PI's time and full-time coordinator*): 80% of the PGY1 research half day will be used to conduct the study. Additional time may be required afterwards, in which case 10-20% of residents' time will be used to complete the study.
- f. Describe the plan for ensuring that all investigators/staff assisting in this research are adequately informed of: 1) the protocol, including revisions to protocol and other study specific changes, 2) investigational product information if applicable, and 3) study related duties and functions: Regular meeting will be held to ensure all participants are on the same page. All members will be informed of changes to the protocol or study.
- g. Describe the facilities available to conduct this research: The patients will undergo shear wave elastography imaging at the radiology department using the latest equipment to conduct such testing. This will take place at the AEMC. We will also use AECIS to access pathology reports and patients' demographics.
- h. If applicable, describe the availability of medical or psychological resources that subjects might need as a result of the anticipated consequences of this research: Written and informed consent will be obtained from all the patients. In order to ensure the subject's understanding, they will be given the opportunity to ask as many questions as necessary. Furthermore, the consenting team will use "teach back" to assess the subjects' understanding of the study's purpose and protocol.

## 6) Study Design

### a. Recruitment Methods:

- i. Describe when, where, and how potential subjects will be recruited (*Describe the source of subjects. Describe the methods that will be used to identify potential subjects. Describe materials, such as advertisements, that will be used to recruit subjects (include these with submission materials. If study is a chart review, describe which records will be accessed to collect data and how you will access them* : A list of patients who recently underwent a native kidney biopsy will be obtained from the pathology department on a weekly basis. Our research team will then contact the patients and discuss participation in the project. If they agree, during a follow up visit with the nephrologist formal informed consent will be obtained and questions answered)
- ii. Will payments to subjects be provided?

NUMBER	DATE	PAGE
HRP-204	12/27/2012	5 of 13

- Yes, amount and timing: 25\$ (cash) at the visit for the shear wave elastography measurements  
 No  
 N/A

**b. Inclusion and Exclusion Criteria:**

- i. Describe how you will screen for eligibility (e.g. review charts, perform specific screening tests, etc.): Adults over the age of 18 who underwent native kidney biopsy at the Einstein Medical Center in Philadelphia will be eligible for the study
- ii. Describe the criteria that define who will be included or excluded in your final study sample:  
 Patients will be excluded for the following conditions:
  - BMI > 35
  - Patients with polycystic kidney disease, renal cell carcinoma, hydronephrosis or renal stones.
  - Patients who develop severe post biopsy complications (infection, significant bleeding requiring transfusion or intervention)
  - Pregnant patients.

**c. Study Timelines:**

- i. Duration of an individual subject's participation in the study: 2-3 months
- ii. Time period anticipated to enroll all study subjects or to complete chart review: 9 months
- iii. Estimated overall study duration (*i.e. from initiation to completion of primary analyses*): 12 months

**d. Study Endpoints:**

- i. Describe the primary and secondary study endpoints (*i.e. the outcome(s) that the study is designed to evaluate*): The primary outcome measure of this study is to determine whether tissue elasticity determined by SWE can assess kidney fibrosis.
- ii. Describe any primary or secondary safety endpoints (*e.g. any disease or symptom that would result in the withdrawal of that subject from the study*): N/A

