**e. Human Research Methods:**

- i. Describe and explain the study design (*e.g. randomized, double-blind, placebo-controlled clinical trial or retrospective chart review*): Prospective cross-sectional study.
- ii. Describe all research activities involved in this protocol, including a study visit timeline if appropriate: We will collect data on consecutive patients with the aim to have 10 patients in each fibrosis group (0-3). After consent, patients will be scheduled to come for a renal ultrasound and SWE. SWE examination will be conducted using an ultrasound machine equipped with a Philips Epiq ARFI Shear wave ElastPQ C1-5 mHz transducer. Shear wave

	AEHN Protocol/Summary		
	NUMBER	DATE	PAGE
	HRP-204	12/27/2012	6 of 13

velocity will be obtained and an estimate of tissue elasticity (Young's modulus) will be calculated. All measurements will be performed by one of two qualified radiology physicians who will be blinded to the clinical and pathological data. We will allow a period of 90 days to obtain the images after the biopsy; otherwise the patient is no longer eligible to participate.

- iii. Identify which tests/procedures are being administered solely for research purposes and which are being conducted as part of standard of care (i.e. procedures that would be done even if the participant were not involved in research): A renal ultrasound will be done as standard of care prior to any kidney biopsy. The shear wave elastography measurement will be done for research purposes.
- iv. Describe steps taken to lessen the probability or magnitude of risks associated with tests/procedures being done for research purposes only (e.g. only appropriately trained personnel involved in procedures, extra tests being done for safety purposes): The shear wave elastography testing is harmless and painless with no implications on patients. Zero radiation exposure.
- v. Describe alternative treatments that are available to subjects if they choose not to participate in research: N/A
- vi. Describe the source records that will be used to collect data: AECIS will be used to obtain demographic data about the patients as well as laboratory values.

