#### **g. Data Management**

- i. Describe steps that will be taken to secure the data (e.g. training, authorization of access, password protection, encryption, physical controls, certificates of confidentiality and separation of identifiers and data) during storage, use and transmission: A master list of MRNs of patients meeting the criteria will be composed. Each patient will then be assigned a study ID number. All information will be tabulated and kept as a data collection file which will not contain identifiers. All eligible patient data will be numbered and analyzed. The information will be stored on a secure HIPPA compliant folder on an Einstein computer as a password protected file. Upon completion of all necessary information on file, the master list with identifiers will be deleted.
- ii. Describe the data analysis plan, including any statistical procedures and method for determining the sample size for the study: Descriptive statistics will be used to summarize the patient characteristics. Data for continuous variables will be presented as mean + SD and categorical variables as numbers and percentages. Linear regression analysis will be performed to describe the relation of the extent of fibrosis and parenchymal stiffness. Stiffness values of patients with different fibrosis grades will be compared using the Mann-Whitney U-test. Statistical analyses will be performed using JMP version 9.0 (Cary, North Carolina, USA).
- iii. Describe where and how data will be stored locally: Data will be stored on a shared drive as a password protected file with access only to members of the research team.
- iv. Specify how long data will be stored locally: 6 years.
- v. Specify who will have access to the data locally: Participants in this research project only

 
Einstein HEALTHCARE NETWORK
	AEHN Protocol/Summary		
	NUMBER	DATE	PAGE
	HRP-204	12/27/2012	8 of 13

- vi. Describe process that will be followed to ensure accuracy of collected data: **Renal ultrasound and shear wave elastography measurements will be performed by an experienced radiologist with over 10 years of ultrasound imaging experience.**
- vii. Will data be sent out or received:  No  Yes
  - a. Who is responsible for receipt or transmission of the data? **N/A**
  - b. How will the data be transported? **N/A**

**h. Provisions to monitor the data for the safety of subjects (Required only when Human Research involves more than minimal risk):**

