## **8) Potential Benefits to Subjects**

- a) Describe the benefits that individual subjects may experience (include when possible the probability, magnitude and duration of the potential benefits) or indicate if there is no direct benefit: The subjects will not benefit. However, determining whether shear wave elastography measurements can predict the degree of fibrosis in diseased kidneys can be of great clinical significance. This may reduce the rates of unnecessary biopsies and eliminate the complications associated with such an invasive procedure.

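### The primary outcome asks whether SWE can assess fibrosis, but no estimate with a confidence interval is designated for it and no measure of separation is planned

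*Combined protocol and SAP*

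**What the plan says.** All references are to the combined protocol and SAP.

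- **Primary outcome (6d i):** "The primary outcome measure of this study is to determine whether tissue elasticity determined by SWE can assess kidney fibrosis". No effect measure, interval or basis for a positive answer is attached.
- **Objective (section 2):** "To determine whether differences exist in elasticity measurements between native kidneys with and without fibrosis".
- **Hypothesis (section 2):** "Kidneys with higher grades of fibrosis will demonstrate higher (up to x 1.5) measures of tissue elasticity and stiffness", relative to kidneys with no fibrosis. The 1.5 is an upper limit and does not reappear in 6d i or 6g ii.
- **Analysis plan (6g ii):** descriptive summaries (mean and SD, numbers and percentages), then "Linear regression analysis will be performed to describe the relation of the extent of fibrosis and parenchymal stiffness" and "Stiffness values of patients with different fibrosis grades will be compared using the Mann-Whitney U-test". Neither analysis is labelled primary. No confidence interval, ROC curve, AUC, sensitivity or specificity is mentioned.
- **Group sizes (5b i and 6e ii):** 40 patients, with the aim of 10 in each of fibrosis grades 0 to 3.
- **Wider claims:** section 3 gives the goal as "to determine whether SWE can be used as a non-invasive marker of kidney fibrosis", and section 8 speaks of "determining whether shear wave elastography measurements can predict the degree of fibrosis in diseased kidneys". These are background and benefits text, but they show how 6d i is likely to be read.

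**The concern.** A difference between groups and the ability to assess fibrosis in a patient are separate questions. Two groups can differ clearly on average while their stiffness values overlap so much that one measurement says little about the kidney in front of the clinician. The planned analyses are suited to the first question, and 6d i asks the second.

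Because 6d i does not say which estimate answers it, the investigators would be free after seeing the data to rest the primary conclusion on whichever result looks best, including a significant test with no statement of how well SWE separates the groups. Section 3 presents SWE as a marker to help decide about biopsy, so a reader would take a positive primary conclusion as a statement about separation.

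**Working it through.** **Check of the plan's own figure.** 4 grades × 10 patients = 40, which matches 5b i. If the aim in 6e ii is met, the objective's contrast is 10 (grade 0) against 30 (grades 1-3). That grouping is implied by the objective and is not written out.

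**Assumptions not in the documents.** Two-sided 0.05 (no level is stated), no tied values, and exactly 10 per grade.

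**Step 1. What a just-significant Mann-Whitney test guarantees.** The observed AUC equals U/(n1 × n2), or one minus that for the smaller U.
- For 10 v 30, n1 × n2 = 300. The largest U that is significant in the exact test is 87 (p = 0.0498).
- Observed AUC = 1 − 87/300 = 0.71.

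**Step 2. Its 95% CI (Hanley-McNeil, 30 with fibrosis as the positive group, 10 without).** SE² = [A(1 − A) + (n1 − 1)(Q1 − A²) + (n0 − 1)(Q2 − A²)]/(n1 × n0), where in this formula Q1 = A/(2 − A) and Q2 = 2A²/(1 + A).
- A = 0.71: Q1 = 0.5504, Q2 = 0.5896, A² = 0.5041.
- SE² = (0.2059 + 29 × 0.0463 + 9 × 0.0855)/300 = 0.0077, so SE = 0.088.
- 0.71 ± 1.96 × 0.088 gives 0.54 to 0.88.

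**Step 3. The same boundary for the regression (n = 40).** The critical t on 38 df is 2.024.
- R² = 2.024²/(2.024² + 38) = 0.10, so r = 0.31.
- The Fisher z 95% CI for r is 0.00 to 0.57.

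Steps 1 to 3 give the least that significance guarantees. They do not predict the result.

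**Step 4. Precision of the proposed estimate.** At A = 0.80 with 10 v 30:
- SE² = (0.16 + 29 × 0.0267 + 9 × 0.0711)/300 = 0.0052, so SE = 0.072.
- 1.96 × SE = 0.14, giving 0.66 to 0.94.

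**Step 5. Does the ×1.5 hypothesis settle separation? (Illustration only.)** The documents give no SD. Assume normal data with equal SD and a coefficient of variation (CV, SD divided by the grade 0 mean) of 0.3, 0.4 or 0.5. Then d = 0.5/CV at ×1.5, and AUC = Φ(d/√2).

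| Assumed pattern | CV 0.3 | CV 0.4 | CV 0.5 |
|---|---|---|---|
| ×1.5 in every fibrosed kidney | 0.88 | 0.81 | 0.76 |
| Linear rise to ×1.5 at grade 3, equal numbers in grades 1-3 | 0.77 | 0.72 | 0.68 |

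A log-normal model with the full ×1.5 ratio gives 0.84, 0.77 and 0.73 at the same CVs. So even if the hypothesis is true, separation could be modest or good.

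**Step 6. Dependence on grade mix (linear rise, CV 0.4 assumed).** The AUCs against grade 0 are 0.616, 0.722 and 0.812 for grades 1, 2 and 3.
- 10/10/10 patients in grades 1/2/3: (0.616 + 0.722 + 0.812)/3 = 0.72.
- 20/5/5: (20 × 0.616 + 5 × 0.722 + 5 × 0.812)/30 = 0.67.
- 5/5/20: (5 × 0.616 + 5 × 0.722 + 20 × 0.812)/30 = 0.76.

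**The case against.** The strongest reply is that 6d i is loose wording for the section 2 objective. Section 4 of the form aside, the background says the team wants to replicate transplant studies that showed an association, and the planned regression and Mann-Whitney tests do address a difference or association. On that reading a missing AUC is not a defect. This stands in part: it is why rewording 6d i is an acceptable remedy. It does not remove the mismatch while 6d i keeps its present wording.

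Three stronger readings are tempting, and the documents do not support them.
- *The planned analyses fail the objective.* They do not; they fit section 2.
- *The plan will judge success by a p-value and report no effect size.* Section 6g ii states no p-value rule or significance level. It says the regression will describe a relation, which is the language of estimation, and a regression yields a slope. What is missing is the designation of an estimate and its interval.
- *SWE will separate the groups poorly.* The documents give no SD, so this cannot be derived. The AUC of 0.71 is a boundary that would apply to any study of this size at the assumed level.

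It is also fair that an AUC from 40 patients may be uninformative. At CV 0.5 with a linear rise, 0.678 ± 0.181 runs from about 0.50 to 0.86. That limits what can be claimed, and it is a reason to show the interval.

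**Conclusion.** The point holds in this form: the primary outcome in 6d i is broader than the objective in section 2, the 6g ii analyses address the narrower question, and neither a designated estimate with an interval nor a measure of separation supports the broader one. A just-significant 10 v 30 Mann-Whitney test guarantees only an observed AUC of about 0.71, with an interval from 0.54, close to no separation. That alone would not support a positive answer to 6d i.

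The textual gap depends on no assumption. The 0.71 depends on the two-sided 0.05 level, no ties and 10 per grade. The CV-based figures are illustrations, and the conclusion does not rest on them. The change should be made, but its absence does not invalidate the study.

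**What to change.** **In 6g ii**, name one primary estimate: the AUC of Young's modulus for grade 0 against grades 1-3, computed as U/(n1 × n2), with its 95% CI and the number of patients in each grade beside it. Report the slope from the planned regression with its 95% CI as supportive. Label any other grade split or any cut-off exploratory.

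**In 6d i**, state that the primary conclusion rests on that estimate and interval.

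**Alternative.** If the sponsor does not want the AUC as primary, word 6d i as a difference or association, matching section 2, and claim no more than that.

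**Cost.** A few sentences, one added output and an interval on a regression already planned; no extra data, procedures or patients. The AUC will be imprecise (about ±0.14 at 0.80 with 10 v 30) and will shift with the achieved mix of grades 1-3, which consecutive enrolment does not control. A positive claim becomes harder to make. The alternative costs only wording, but gives up the broader claim.
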